7.5 Breaking Codes in Double-Blinded Studies

The treatment code cannot be broken except in the event of an emergency for an individual patient.

In the event of an emergency, call the ACCRU Registration Office at [REDACTED] to break the code on Monday through Friday, 8:00 a.m. to 4:30 p.m. Central Time. If the code must be broken after hours, assume the patient was assigned to active treatment and treat accordingly. Place a call to the ACCRU Registration Office and leave a message informing them of the need to un-blind a patient. Provide your contact information so that ACCRU Registration Office personnel can return the call the next business day.

If in the judgement of the attending physician, it would be helpful for the future clinical care of the individual patient, the code may be broken after the patient has completed the study. That is, after the patient has been fully evaluated and all evaluation information has been recorded by the attending physician and the patient (if appropriate), the ACCRU Registration Office may be called to find out which study therapy the patient was receiving.

## 8.0 Dosage Modification Based on Adverse Events

For all adverse events reported in this study considered at least partly causal to the administration of selumetinib, the following dose modification guidance should be applied.

**ALERT:** *ADR reporting may be required for some adverse events (See Section 10)*

8.1 Dose Levels (Based on Adverse Events in Section 8.2)

Dose Level	Selumetinib
0	75 mg PO BID
-1	50 mg PO BID

Dose level 0 refers to the starting dose.

8.2 Guidelines for Dose Modifications/Interruptions

For adverse events (AEs) that are considered at least partly due to administration of selumetinib

the following dose reduction/adjustment guidance may be applied:

Treatment with selumetinib/placebo should be temporarily interrupted if one of the following adverse events occurs **despite optimal supportive care**:

- Any intolerable adverse event regardless of grade
- Any adverse events  $\geq$  CTCAE Grade 3 (despite optimal supportive care) (exception: patients with  $\geq$  Grade 3 lymphopenia or asymptomatic biochemistry laboratory abnormalities may be continued on study treatment at the same dose level without interruption based upon investigator judgment).

On improvement of the adverse event to CTCAE grade 1 (or to CTCAE grade 2 for rash) or baseline, selumetinib may be restarted at the same dose or may be reduced as described in section 8.1 at the discretion of the investigator. One dose reduction is allowed before permanent discontinuation of therapy.

- If a further episode of the same AE subsequently requires dose interruption, selumetinib may be restarted at the next dose level down on improvement of the AE.
- If a different AE subsequently requires dose interruption, selumetinib may be restarted at the same dose or at the next dose level down on improvement of the AE.
- Selumetinib should not be re-escalated to an earlier dose level on improvement of an AE.
- Ideally, placebo or selumetinib dosing/treatment should be maintained for at least 7 days prior to and throughout administration of therapeutic  $^{131}\text{I}$ ; however, this is not a requirement. If necessary, study procedures and/or  $^{131}\text{I}$  therapy may be rescheduled/repeated ( $^{131}\text{I}$  therapy should be administered only once) at the discretion of the investigator to achieve this. Extending the time on placebo or selumetinib (i.e. extending time on treatment and/or instituting treatment interruptions) and/or rescheduling protocol assessments/treatments is allowed in order to comply with this approach at the investigator's discretion.
- The period of time on placebo or selumetinib (i.e. extending time on treatment and/or instituting treatment interruptions) is not to exceed 8 weeks.
- NOTE: missing less than 7 doses of placebo or selumetinib for reasons other than toxicity will not be considered a violation of the protocol.

## 9.0 Ancillary Treatment/Supportive Care

All management of adverse events is left to the Investigator's discretion. **Appendix IV** includes guidelines for the management of some common selumetinib-related adverse events. Compliance with those guidelines is recommended, but not required.

- 9.1 Antiemetics may be used at the discretion of the attending physician.
- 9.2 Blood products and growth factors should be utilized as clinically warranted and following institutional policies and recommendations. The use of growth factors should follow published guidelines of the American Society of Clinical Oncology Update of Recommendations for the Use of White Blood Cell Growth Factors: An Evidence-Based Clinical Practice Guideline. *J Clin Oncol* 2006; 24:3187-3205.
- 9.3 Patients should receive full supportive care while on this study. This includes blood product support, antibiotic treatment, and treatment of other newly diagnosed or concurrent medical

conditions. All blood products and concomitant medications such as antidiarrheals, analgesics, and/or antiemetics received from the first day of study treatment administration until 30 days after the final dose will be recorded in the medical records.

9.4 **Rash**: early initiation of treatment for rash is strongly recommended to minimize the duration and severity of the adverse event. All patients should be given emollient cream to take home for prophylactic use once study treatment has been initiated (see **Appendix IV**).

9.5 **Diarrhea**: early initiation of treatment for diarrhea is strongly recommended to minimize the duration and severity of the adverse event. Treatment provision will be according to Investigator discretion according to local practice and regulations (see **Appendix IV**).

9.6 **Dyspnea**: new or worsening dyspnea has been reported during treatment with selumetinib; investigation to determine the underlying cause is recommended (see **Appendix IV**).

9.7 **Reduction in LVEF**: asymptomatic reductions in LVEF have been reported in some patients receiving selumetinib; treatment may be recommended depending on the magnitude of the LVEF reduction (see **Appendix IV**).

9.8 **Visual disturbances**: symptoms, including blurred vision, occur commonly during treatment with selumetinib, and AEs of central serous retinopathy and retinal vein occlusion have been reported in studies of other MEK inhibitors. Investigation to determine the underlying cause of visual disturbance is recommended, including ophthalmological examination. Patients with an ongoing retinal abnormality at the time of selumetinib discontinuation should have a follow-up ophthalmological assessment approximately 28 days after discontinuation. This assessment is recommended to document reversibility, but should be performed only if the patient is fit enough to have the assessment (see **Appendix IV**).

Extra assessments are recommended for investigation of specific adverse events that occur during treatment with selumetinib:

Adverse event	Assessment
Clinically significant LVEF reduction (by <math>\geq 10</math> percentage points and to below 55%)	Single ECG Troponin levels (isoform according to institutional norm)
Cardio-respiratory AEs of non-obvious cause	Single ECG Troponin levels (isoform according to institutional norm)
New or worsening respiratory symptoms (such as dyspnea, cough)	Single ECG

## 10.0 Adverse Event (AE) Reporting and Monitoring

### 10.1 Adverse Event Characteristics

**CTCAE term (AE description) and grade**: The descriptions and grading scales found in the revised NCI Common Terminology Criteria for Adverse Events (CTCAE) version 4.0 will be

utilized for AE reporting. All appropriate treatment areas should have access to a copy of the CTCAE version 4.0. A copy of the CTCAE version 4.0 can be downloaded from the CTEP web site: ([http://ctep.cancer.gov/protocolDevelopment/electronic\\_applications/ctc.htm](http://ctep.cancer.gov/protocolDevelopment/electronic_applications/ctc.htm))

10.11 Adverse event monitoring and reporting is a routine part of every clinical trial. First, identify and grade the severity of the event using the CTCAE version 4.0. Next, determine whether the event is expected or unexpected (see Section 10.2) and if the adverse event is related to the medical treatment or procedure (see Section 10.3). With this information, determine whether the event must be reported as an expedited report (see Section 10.4). Expedited reports are to be completed within the timeframes and via the mechanisms specified in Sections 10.4. All AEs reported via expedited mechanisms must also be reported via the routine data reporting mechanisms defined by the protocol (see Sections 10.5 and 18.0).

10.12 Each CTCAE term in the current version is a unique representation of a specific event used for medical documentation and scientific analysis and is a single MedDRA Lowest Level Term (LLT).

**NOTE:** A severe AE, as defined by the above grading scale, is **NOT** the same as serious AE which is defined in the table in Section 10.4.

#### 10.2 Expected vs. Unexpected Events

- The determination of whether an AE is expected is based on agent-specific information provided in Section 15.0 of the protocol.
- Unexpected AEs are those not listed in the agent-specific information provided in Section 15.0 of the protocol.

**NOTE:** “Unexpected adverse experiences” means any adverse experience that is neither identified in nature, severity, or frequency of risk in the information provided for IRB review nor mentioned in the consent form.

#### 10.3 Assessment of Attribution

*When assessing whether an adverse event is related to a medical treatment or procedure, the following attribution categories are utilized:*

Definite - The adverse event *is clearly related* to the agent(s).  
Probable - The adverse event *is likely related* to the agent(s).  
Possible - The adverse event *may be related* to the agent(s).  
Unlikely - The adverse event *is doubtfully related* to the agent(s).  
Unrelated - The adverse event *is clearly NOT related* to the agent(s).

**Events determined to be possibly, probably or definitely attributed to a medical treatment suggest there is evidence to indicate a causal relationship between the drug and the adverse event.**

10.31 **Special Situations for Expedited Reporting****Exceptions to Expedited Reporting: EXPECTED Serious Adverse Events**

An expedited report may not be required for specific Grade 1, 2 and 3 Serious Adverse Events where the AE is **EXPECTED**. Any protocol specific reporting procedures MUST BE SPECIFIED BELOW and will supersede the standard Expedited Adverse Event Reporting Requirements:

System Organ Class (SOC)	Adverse event/ Symptoms	CTCAE Grade at which the event will not be expeditiously reported.
General disorders and administration site conditions	Edema face	$\leq$ Grade 3
	Edema trunk	
	Fatigue	
	Fever	
Skin and subcutaneous tissue disorders	Dry skin	$\leq$ Grade 3
	Rash acneiform	
	Rash maculo-papular	
	Stevens-Johnson syndrome	
Respiratory, thoracic and mediastinal disorders	Dyspnea	$\leq$ Grade 3
Eye disorders	Blurred vision	$\leq$ Grade 3
Vascular disorders	Hypertension	$\leq$ Grade 3
Investigations	Alanine aminotransferase increased	$\leq$ Grade 3
	Aspartate aminotransferase increased	
Gastrointestinal disorders	Diarrhea	$\leq$ Grade 3
	Nausea	
	Vomiting	
	Mucositis oral	
	Dry mouth	
Infections and infestations	Nail infection	$\leq$ Grade 3

Specific protocol exceptions to expedited reporting should be reported expeditiously by investigators **ONLY** if they exceed the expected grade of the event.

These exceptions only apply if the adverse event does not result in hospitalization. If the adverse event results in hospitalization, then the standard expedited adverse events reporting requirements must be followed.

The following hospitalizations are not considered to be SAEs because there is no “adverse event” (*i.e.*, there is no untoward medical occurrence) associated with the hospitalization:

- Hospitalizations for respite care
- Planned hospitalizations required by the protocol or to administer protocol-directed treatment (*i.e.*  $^{131}\text{I}$  therapy)
- Hospitalization planned before informed consent (where the condition requiring the hospitalization has not changed post study drug administration)
- Hospitalization for administration of study drug or insertion of access for administration of study drug
- Hospitalization for routine maintenance of a device (*e.g.*, battery replacement) that was in place before study entry

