##### **Common Adverse Events, (1 to <10%)**

Cardiovascular: Hypertension

Central nervous system: Fever, dizziness, insomnia, depression

Dermatologic: Dry skin, pruritus, rash

Endocrine & metabolic: Hypoalbuminemia, hypomagnesemia, hyperphosphatemia

Eye: Periorbital edema, blurred vision

Gastrointestinal: upper abdominal pain, abdominal distension, stomatitis, anorexia, decreased appetite, dry mouth

Hematologic: Thrombocytopenia, anemia

Hepatic: AST increased, ALT increased

Neuromuscular & skeletal: Back pain, arthralgia, asthenia

Respiratory: Dyspnea, cough

Miscellaneous: Alopecia, Low blood potassium

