##### **Rare Adverse Events (Important or life-threatening), <1%**

Left ventricular systolic dysfunction, Liver injury/failure

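### Section 10.31 exempts Stevens-Johnson syndrome at Grade 3 or below from expedited reporting as expected, but Section 15.0 does not list it; the gap is serious Grade 3 cases without hospitalisation

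*Combined protocol and SAP*

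**What the plan says.** Section 10.11 sets the order of work: grade the event, decide under Section 10.2 whether it is expected, judge attribution, then decide whether an expedited report is due.

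Section 10.2 gives the test for expectedness: "The determination of whether an AE is expected is based on agent-specific information provided in Section 15.0 of the protocol". The converse follows: "Unexpected AEs are those not listed in the agent-specific information provided in Section 15.0 of the protocol". A NOTE in the same section words it differently, describing an unexpected experience as one "neither identified in nature, severity, or frequency of risk in the information provided for IRB review nor mentioned in the consent form".

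Section 10.31 sets out the waiver: "An expedited report may not be required for specific Grade 1, 2 and 3 Serious Adverse Events where the AE is" expected (that last word is in bold capitals in the protocol). It adds that protocol-specific procedures listed there override the standard expedited requirements. The grade column of its table is headed "CTCAE Grade at which the event will not be expeditiously reported", and the skin block, which includes "Stevens-Johnson syndrome", carries the entry Grade 3 or below. Listed terms are to be expedited only above that grade. The exemption lapses if the event leads to hospitalisation.

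Section 10.41 holds the standard timelines and refers to Section 10.31 for exceptions.

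Section 15.17 is the toxicity list. Its common skin entry is "Dermatologic: Dry skin, pruritus, rash", and its list of rare but important or life-threatening events is "Left ventricular systolic dysfunction, Liver injury/failure".

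**The concern.** The waiver depends on an event being expected, and the protocol says where expectedness is to be looked up. A term that is in the exemption table but not in the look-up list gives the site two opposite answers. A coordinator who reads Section 10.2 classes Stevens-Johnson syndrome as unexpected and reports it. One who reads the Section 10.31 table finds it named as exempt and does not.

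At stake is how quickly a serious skin reaction reaches the sponsor in a double-blind trial. An expedited report goes to the safety office and from there to the IND coordinator. The drug supplier is copied when a regulatory report is made. If no expedited report is sent, that chain does not start.

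**Working it through.** No sample-size or event-rate arithmetic applies. The check compares the sections and then works out which cases are affected.

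**Step 1: is the term in Section 15.0?** The skin terms in Section 15.17 are:
- very common: acneiform rash and maculo-papular rash;
- common: dry skin, pruritus and rash, with alopecia under Miscellaneous;
- rare, important or life-threatening: none. The only two entries are left ventricular systolic dysfunction and liver injury/failure.

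The nursing guidelines in Section 15.19 mention acneiform rash and alopecia. Stevens-Johnson syndrome appears nowhere in Section 15.0. It is also absent from the rash terms and the pilot-study toxicities in Section 1.0. The Section 10.31 table is its only mention in the available text.

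**Step 2: the rest of the table.** The Section 10.31 table has 19 terms. Fourteen appear by name in Section 15.17. One more, oral mucositis, matches stomatitis in substance but not in name. That leaves 19 − 14 − 1 = 4: Stevens-Johnson syndrome, edema face, edema trunk and nail infection. Under strict name matching the count is 5.

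**Step 3: which cases change?** Reading the Section 10.41 table against the exemption, for a serious event:

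| Case | Section 10.41 | With the exemption followed | Changed? |
|---|---|---|---|
| Grade 1–2, not hospitalised | not required | not required | no |
| Grade 3, not hospitalised | 7 calendar days | no expedited report | **yes** |
| Grade 1–3, hospitalised | 7 calendar days | 7 calendar days (exemption lapses) | no |
| Grade 4–5 | 24 hours, full report within 3 more calendar days | same (above exempt grade) | no |

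Only one row changes. This assumes that the Grade 3 entry, printed once per block, covers every term in that block, which is the natural reading of a merged cell. It also assumes that the spanning cells of the Section 10.41 table have been read correctly.

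**Step 4: do other routes replace the 7-day report?**
- Section 10.522 puts Grade 3 events on the case report form whatever their attribution, but this is routine data flow with no 7-day limit.
- Section 16.8 gives the study team real-time notice of Grade 4 and 5 events only, and DSMB review at least twice a year.
- Section 10.311 requires immediate reporting of events causing persistent or significant incapacity. That covers some Grade 3 outpatient cases. It does not cover one that is serious only as an important medical event.

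**The case against.** **A second definition.** The NOTE in Section 10.2 ties unexpected to the information given to the IRB and to the consent form, and Section 15.0 opens by pointing to the Investigator's Brochure. Neither the consent form nor the brochure is in the available text. If either names the syndrome, it may count as expected under the NOTE. This stands as a limit on the finding. It does not remove the conflict, because the Section 15.0 rule is explicit and Section 15.0 would still disagree with Section 10.31.

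**The waiver may defeat itself.** Section 10.31 is conditional on expectedness and says only that a report may not be required. If the syndrome is unexpected under Section 10.2, the condition fails and Section 10.41 could still apply. Section 10.41 also tells investigators to report any serious event to the sponsor immediately, although it then defers to Section 10.31. So the documents support saying that a case can go unexpedited, not that it certainly will.

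**Readings that go too far.** A reader might infer any of the following, and the documents support none of them:
- All Stevens-Johnson syndrome up to Grade 3 loses expedited reporting. Step 3 shows that only the non-hospitalised Grade 3 case changes.
- The roughly 70% rash frequency in Section 1.0 indicates the risk. That figure pools other rash terms from phase II studies of the 100 mg suspension, and the documents give no frequency for this syndrome.
- Every exempt term missing from Section 15.17 should be struck. Facial edema is reported in Section 1.0, at 4% in the phase II studies and 10% in the pilot, so for that term Section 15.17 may be the incomplete list.

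**Conclusion.** The inconsistency is real and narrow. Section 10.31 treats Stevens-Johnson syndrome as expected, while the Section 15.0 rule in Section 10.2 makes it unexpected. Followed as written, the table moves a serious Grade 3 case without hospitalisation from a 7-calendar-day report to none, and no other route in the protocol fully replaces that report.

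The conclusion rests on the Section 15.0 rule. Status under the NOTE in Section 10.2 is unknown. No endpoint or sample size is affected, and the adverse-event stopping rules in Section 16.8 count Grade 4 and 5 events only. The data are not lost, since Grade 3 events still reach the case report form; what is lost is speed. The change should be made because it concerns safety reporting and is cheap.

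**What to change.** Remove Stevens-Johnson syndrome from the Section 10.31 exemption table, so that the Section 10.41 timelines apply to it without argument.

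For edema face, edema trunk and nail infection, reconcile Section 10.31 with Section 15.17. Either add each term to Section 15.17 if it is expected, for which facial edema has support in Section 1.0, or remove its exemption. Oral mucositis needs at most a wording match with stomatitis.

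The cost is one edit to the Section 10.31 table, at most a few added terms in Section 15.17, and possibly a few more expedited reports.

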#### **10.311 Persistent or Significant Disabilities/Incapacities**

Any AE that results in persistent or significant incapacity or substantial disruption of the ability to conduct normal life functions (formerly referred to as disabilities), congenital abnormalities or birth defects, must be reported immediately if they occur at any time following treatment with an agent under an IND/IDE since they are considered to be a serious AE and must be reported to the sponsor as specified in 21 CFR 312.64(b).

#### **10.312 Death**

- Any death occurring within 30 days of the last dose, regardless of attribution to an agent/intervention under an IND/IDE requires expedited reporting within 24-hours.
- Any death occurring greater than 30 days with an attribution of possible, probable, or definite to an agent/intervention under an IND/IDE requires expedited reporting within 24-hours.

##### **• Reportable categories of Death**

- Death attributable to a CTCAE term.
- Death Neonatal: A disorder characterized by cessation of life during the first 28 days of life.
- Death NOS: A cessation of life that cannot be attributed to a CTCAE term associated with Grade 5.
- Sudden death NOS: A sudden (defined as instant or within one hour of the onset of symptoms) or an unobserved cessation of life that cannot be attributed to a CTCAE term associated with Grade 5.
- Death due to progressive disease should be reported as **Grade 5 “Neoplasms benign, malignant and unspecified (incl cysts and polyps) – Other (Progressive Disease)”** under the system organ class (SOC) of the same name. Evidence that the death was a manifestation of underlying disease (*e.g.*, radiological changes suggesting tumor growth or progression; clinical deterioration associated with a disease process) should be submitted.

10.313 **Secondary Malignancy**

- A *secondary malignancy* is a cancer caused by treatment for a previous malignancy (e.g., treatment with investigational agent/intervention, radiation or chemotherapy). A secondary malignancy is not considered a metastasis of the initial neoplasm.
- All secondary malignancies that occur following treatment with an agent under an IND/IDE to be reported. Three options are available to describe the event:
  - Leukemia secondary to oncology chemotherapy (e.g., Acute Myelocytic Leukemia [AML])
  - Myelodysplastic syndrome (MDS)
  - Treatment-related secondary malignancy
- Any malignancy possibly related to cancer treatment (including AML/MDS) should also be reported via the routine reporting mechanisms outlined in each protocol.

10.314 **Second Malignancy**

- A second malignancy is one unrelated to the treatment of a prior malignancy (and is NOT a metastasis from the initial malignancy). Second malignancies require ONLY routine reporting.

